	1.0	27.11.2019	[name]	First complete protocol draft. Submitted for IRB review but withdrawn by the research team for further edits	29.11.2019	Withdrawn	N / A	N / A
1	2.0	17.12.2019	[name]	Expanded the trial area: Earlier only Kayes region, now parts of Kayes, Kita, and Koulikoro regions. Removed the bridging trial after interim analysis Cut out the last 6 calendar months of follow-up in the trial. Half of the clusters now followed up for 8 MDA rounds, 30% for 7 MDA rounds and 20% for 6 MDA rounds Increasing sample size from 650 to 750 mortality analysis clusters Changed the ratio of control vs azi-biannual vs azi quarterly clusters from 1 : 1 : 1 to 3 : 4 : 2 Reduced the number of interim analyses from 2 to 1 – to be done at approximately 60% of the data accrual Changed the timing of AMR and other biological sample collection slightly Added a second field laboratory to Koulikoro region Expanded the area of a possible MDA roll-out area to 3-5 regions, including the entire Kayes, Kita and Koulikoro, and possibly parts of Bougouni and Segou.	17.12.2019	27.12.2019	13.01.2020	04.02.2020
2	3.0	08.03.2022	[name], [name], [name]	Increased sample size from 830 to 1150 clusters (or 35,650 infants treated on MDA1, whichever comes first), because of lower-than-expected numbers of infants / cluster and baseline mortality. Edited assumptions behind the sample size selection. Changed the plan of primary analysis, to include mortality data also from the secondary outcome sample. Clarified the process of code breaking before primary analysis	15.3.2022	28.3.2022		

AMENDMENT NO.	PROTOCOL VERSION #	DATE ISSUED	AUTHOR/S OF CHANGES	DETAILS OF CHANGES MADE	SUBMITTED TO IRB, MALI (DATE)	APPROVED AT IRB, MALI (DATE/NO)	SUBMITTED TO IRB, TAU (DATE)	APPROVED AT IRB, TAU (DATE/NO)
				
Extended the duration of cluster enrolment from 52 to 78 weeks
 
Removed the inclusion of a tertiary AMR sample
 
Changed the timing for AMR analyses to include samples at baseline, and at 12, 24, ad 36 months after baseline
 
Clarified the AMR analyses to include resistance to WHO “Access” group antibiotics among azithromycin-resistant bacterial isolates
 
Edited laboratory tests to be done in the mechanistic study: replaced fecal calprotectin measurement with three other fecal biomarkers: neopterin, myeloperoxidase, and alpha 1 antitrypsin
 
Provided more detail on the age of infants eligible for the intervention (aged expressed in days, not only months)
 
Provided further details on possible outcome scenarios for the planned interim analysis
 
Change establishment of a second field site for AMR testing in Koulikoro as optional.
 
Edited participant information document with the updated information on sample size and age of eligible infants
 
Provided detailed instructions regarding study drug administration and referral of children participating in mechanistic substudy for whom blood samples are collected and Hb and CRP levels are measured on site. Added a document that will be used to advise CSCOM personnel on participant management (Appendix 5).
				
3	4.0	27.06.2022	[name], [name], [name]	
Added a tertiary sample for collection of AMR and mechanistic study samples in a subset of villages closer to Bamako, i.e., in the study regions of Koulikoro and Kita.
 
Replaced Norgen Stool Nucleic Acid kit by DESS media (DMSO/EDTA/saturated sodium chloride) for the preservation of second rectal swab collected at AMR study visits.
 
Specified that AMR and mechanistic study samples may be directly transported to CVD-Mali Bamako laboratory for processing.
				

AMENDMENT NO.	PROTOCOL VERSION #	DATE ISSUED	AUTHOR/S OF CHANGES	DETAILS OF CHANGES MADE	SUBMITTED TO IRB, MALI (DATE)	APPROVED AT IRB, MALI (DATE/NO)	SUBMITTED TO IRB, TAU (DATE)	APPROVED AT IRB, TAU (DATE/NO)
				
Changed the timing for mechanistic study data and sample collection to MDA 4 for 4–11-month-old infants, MDA 6–8 and visit 9 for 6- and 12–14-months old infants and children.
 
Edited one hypothesis for the mechanistic study extending the assessment of community-level prevalence of malaria parasitaemia at the end of the intervention (9th visit) to 12–14 months old children.
 
Edited instructions regarding referral of children who have abnormal Hb or CRP values in the mechanistic sub-study. Edited the referral document (Appendix 5).
 
Specified that anthropometric measurements for growth study, and samples collection for mechanistic study will be conducted at the time of the study visits, instead of two weeks later, and possibly in a central location in village.
 
Removed head circumference from growth study outcomes.
 
Changed the target age for morbidity data collection to 4–14 months.
 
Provided further details on how the feasibility study will be done.
 
Added an economic analysis (chapter 4.18).
 
Clarified, based on trial adaptive design, the interim analysis outcomes that will lead trial conduct to be altered.
 
Specified that a 1:1 allocation ratio will be used to re-randomize previous placebo-clusters in the two AZI groups if after interim analysis the placebo arm is dropped.
 
Clarified that random allocation of letter codes to treatment was conducted by the external partner, RTI International, who then provided the code to Pfizer.
 
Clarified that closed-testing procedure will be used to adjust statistical analyses for multiple comparisons.
 
Clarified that analytical method for mechanism study will account for clustering.
				

AMENDMENT NO.	PROTOCOL VERSION #	DATE ISSUED	AUTHOR/S OF CHANGES	DETAILS OF CHANGES MADE	SUBMITTED TO IRB, MALI (DATE)	APPROVED AT IRB, MALI (DATE/NO)	SUBMITTED TO IRB, TAU (DATE)	APPROVED AT IRB, TAU (DATE/NO)
4	5.0	23.03.2023	[name], [name], [name]	
Specified that mechanistic study in tertiary sample will be conducted during rainy season (Peak malaria transmission).
 
Specified that Growth study may be conducted in tertiary sample if planned sample size for the study is not achieved with secondary sample.
 
Specified “Parasite density” as an outcome of mechanistic study to clarify the quantitative aspect of parasitaemia measures besides malaria prevalence.
 
Provided clarification on exploratory analysis and effect modifiers to be tested.
 
Edited one hypothesis for the mechanistic study extending the assessment of community-level prevalence of malaria parasitaemia at the end of the intervention (9th visit) to 1-59 months old children. And, provided further details on sample size and sampling methods, as well as compensation.
 
Edited the Information about Participation in the AMR and other sub-studies to include Kati as one of the CSComs included in the sub studies (tertiary sample).
				
5	6.0	15.12.2023	[name], [name], [name]	
Expanded the age group of children being sampled for AMR analysis at visit 11 to also include 15-26 months old children. Expanding the age group at visit 11 will allow to assess whether carriage of antibiotic resistant bacteria persists in individual children who received 1-4 doses of azithromycin MDA one year prior to sampling and who live in a village that have stopped MDA intervention.
 
Additionally, we will sample 24-35 months old children at visit 9 in the Kati region (tertiary AMR sample). This will determine whether carriage of antibiotic resistant bacteria persist in children who received 1-4 doses of azithromycin MDA one year prior to sampling but live in a village where MDA intervention has continued.
				

AMENDMENT NO.	PROTOCOL VERSION #	DATE ISSUED	AUTHOR/S OF CHANGES	DETAILS OF CHANGES MADE	SUBMITTED TO IRB, MALI (DATE)	APPROVED AT IRB, MALI (DATE/NO)	SUBMITTED TO IRB, TAU (DATE)	APPROVED AT IRB, TAU (DATE/NO)
6	7	13.11.2024	[name], [name]	
Added “hard-to-reach” village status and Strategie Avancée as one of the potential effect modifiers in sections 4 and 5.
 
Included a survey among the field workers as a part of the feasibility aspect.
 
Amended a study question regarding hardness-to-reach and the inclusion of village to Strategie Avancée being a predictor of high mortality (section 4.02.)
 
Amended the aspect of field worker assessment to section 4.18.
				

2. Executive summary

2.02. Key details of the trial

Background:	There is recent evidence that mass-drug administration (MDA) of azithromycin to apparently healthy young children, reduces their mortality in some, but not in all low-income African settings.
Main objective:	To determine the impact of quarterly (given every 3 months) or bi-annual (given twice / year, between January and June) azithromycin MDA to 1–11-month (29-364 days) old infants on their mortality and other health outcomes, when provided in a context of a seasonal malaria chemoprevention (SMC) program.
Trial approach:	A cluster-randomized, placebo-controlled, double-blinded, parallel-group, three-arm clinical trial with adaptive design, in rural and peri-urban villages in the Kayes, Kita, and Koulikoro regions of Mali, Sub-Saharan Africa.
Main methods:	Selected and consenting villages will be randomly allocated into three groups: Control, Azi-quarterly, and Azi-biannual. Households in the participating villages will be visited at quarterly intervals by study staff. At each visit, there will be a census of all household members as well as recording of births and child deaths since the last visit. All 1-11 months old infants (age 29-364 days), for whom there is a consent from a guardian for study drug provision, will be weighed and given a single dose of study drug. Infants in control group will receive placebo at each visit, infants in Azi-bianual group will receive placebo at visits between July and December and 20 mg / kg azithromycin at visits between January and June, and infants in the Azi-quarterly group will receive 20 mg / kg azithromycin at each visit. The village visit will be repeated every 3 months for 8 times for study drug administration and one more time for census and vital statistics recording. SMC with amodiaquine and sulfadoxine-pyrimethamine will be offered through the national health service to all 3–59-month-old children on a monthly basis between July and October in each year.
Primary outcome	Mortality (deaths / 1000 years at risk) among children who were 1–11 month (29-364 days) old at mass azithromycin administration.
Other outcomes	Episodes of ARI, malaria, and diarrhea Infant and young child growth Prevalence of antimicrobial resistance towards azithromycin Malaria parasitemia, inflammation, and immune development Feasibility of azithromycin MDA implementation including economic analysis Incidence of serious adverse events (SAE) and adverse events (AE) Mortality among children, who were 12–59-month-old at the MDA

Adaptive design: One interim analysis will be completed when approximately 60% of the 3-month follow-up intervals have been completed. If there is a statistically significant mortality difference between the quarterly azithromycin group and the placebo group as well as between the biannual azithromycin group and the placebo group but not between the two azithromycin groups, the placebo arm will be discontinued, and trial completed with two arms only. If there is also a statistically significant difference also between the two azithromycin groups, the trial will be stopped, and the team will offer to work with Malian Ministry of Health to provide azithromycin MDA in the trial site and elsewhere in the regions of Mali.

Sample size: Approximately 1150 clusters (villages). At each MDA round, each cluster is expected to contain on average 31 eligible infants who will provide data to the study.

Stored samples: Some vials of frozen plasma, white blood cells, urine and stools and dried blood spots from a sub-group will be stored for later analyses.

3. Background

3.01. Health problem to be addressed

Infant and child mortality in Mali and elsewhere in sub-Saharan Africa.

According to the most recent estimates, 3.0 million infants and children between 1-59 months die each year, mostly from infectious diseases (WHO, 2018). Approximately 1.2 million of these deaths are estimated to take place in Western and Central Africa, 0.7 million in Eastern and Southern Africa, 0.7 million in South Asia, 0.3 million in East Asia and Pacific, and 0.1 million elsewhere (UNICEF, 2017). By 2030, global leaders have committed to ending preventable deaths of children under 5 years of age, with all countries aiming to reduce under-5 mortality to at least as low as 25 per 1,000 live births (United Nations Development Program, 2014).

3.02. Study objective

To determine the impact of quarterly and bi-annual mass azithromycin administration to 1-11 month (29-364 days) old infants in rural and periurban Mali on their mortality and other health outcomes, on mortality of older children, and to assess the feasibility and possible mechanisms of action of the intervention.

3.03. Background to and justification for the study

Azithromycin mass drug administration (MDA) has been used for approximately 20 years to control trachoma, a blinding eye disease. Over 600 million doses of oral azithromycin have been prescribed to children and adults living in areas of active trachoma program (Emerson et al., 2017). In some settings, trachoma control programs with repeated treatment of all community members with azithromycin has been associated with prevention of other infections, such as malaria, diarrhea and pneumonia (Whitty et al., 1999; Fry et al., 2002; Coles et al., 2011; Coles et al., 2012; Gaynor et al., 2014; Schachterle et al., 2014). Two studies in the same community in Ethiopia, one with a case-control design and the other one being a cluster-randomized trial suggested that azithromycin MDA might also be associated with reduced under-five mortality (Porco et al., 2009; Keenan et al., 2011)

Encouraged by the previous results, two randomized controlled trials were implemented recently to test the hypothesis that azithromycin MDA would be associated with reduced mortality among 1-59-month-old children in Sub-Saharan Africa. The first study (MORDOR) was a placebo-controlled trial in Malawi, Tanzania, and Niger. Approximately 1500 clusters were randomly allocated into being either an intervention or a control cluster. In the intervention clusters, all 1-59-month-old children were treated with a single dose of azithromycin every 6 months for two years; in control clusters

children received a respective placebo dose. Neonates, older children and adults were not treated.

In the MORDOR sample, azithromycin treatment was associated with a statistically significant 13.5% overall reduction in mortality among 1–59-month-old children. The difference between intervention and control was approximately 18% in Niger, 6% in Malawi and 3% in Tanzania. The differences were largest among 1–5-month-old children and after the fourth treatment cycle – but there was not enough power to formally test hypotheses about effect modification. Verbal autopsy data suggest that 41% of the deaths were due to malaria, 18% to diarrhea or dysentery and 12% pneumonia (Keenan et al., 2018).

In another trial in Burkina Faso and Mali, researchers tested the impact of combining azithromycin MDA to seasonal malaria chemoprevention (SMC, with sulfadoxine-pyrimethamine and amodiaquine). The intervention was offered monthly to 3–59-month-old children over three consecutive months. In this sample, there was no difference between the trial arms in a combined outcome of hospitalization or death (Chandramohan et al., 2019).

Based on earlier results, it thus seems that azithromycin MDA reduces infant or child mortality in some, but not in all low-income African settings. An expert committee for the World Health Organization has reviewed the data and called for further research, to strengthen the evidence-based on azithromycin MDA. Because of the observed heterogeneity and possible effect modification by SMC or other co-interventions, further trials in new settings are needed in order to make evidence-based public health recommendations about the use of this treatment. Because of a fear for antimicrobial resistance (AMR), there is also a need to investigate if a more limited target group (1–11 months) would alleviate the AMR risk but retain the intervention's impact on mortality. Because the MORDOR data suggested that the mortality benefit is concentrated to the first three months after the MDA dose (Porco et al., 2019), there is also a need for testing the impact of more frequent MDA dosing, on mortality, AMR, and feasibility of the intervention, as compared to the previously tested bi-annual treatment of 1–59-month-old children. Because of the earlier results suggesting limited additional benefit from azithromycin when provided concomitantly with SMC, there is also a need to test the impact of bi-annual dosing that is provided quarterly, but only during seasons when SMC is not offered.

LAKANA trial has been designed to address the health impacts of quarterly and biannual azithromycin MDA when delivered to 1–11-month-old infants in a high-mortality setting where malaria is holoendemic but there is also a functioning SMC program in place. The trial name (LAKANA) is an abbreviation from “Large-scale Assessment of the Key health-promoting Activities of two New mass drug administration regimens with Azithromycin. In Bambara, which is the local language in the study area, LAKANA means “*to protect*” or “*to be safe*”.

3.04. Potential public health effects

The present study may offer a partial solution to a major public health problem in Mali and elsewhere in Sub-Saharan Africa. Should the intervention work, it will significantly contribute to the options for successfully reducing child mortality which is one of the United Nations sustainable development goals. Thus, if the trial provides supportive evidence for a positive mortality benefit by azithromycin MDA, it will form the first phase of a national public health program in Mali. In phase 2, that would still form a part of the currently funded project, an azithromycin MDA program would be rolled out in the regions where the trial is implemented, if the government of Mali considers that desirable. In phase 3, there could be a national roll-out, the details of and funding for which would need to be separately negotiated.

Large-scale use of antibiotics raises always a concern of antimicrobial resistance, which could negatively impact clinical outcomes in the communities in which resistance emerges. Multiple studies have documented relatively rapid emergence of macrolide resistance following mass drug administration with azithromycin (Rogawski et al., 2015) but resistance appears to decline quickly after discontinuation of treatment (Sánchez et al. 1994; Mack et al., 2019) and there is little evidence of AMR spread to individuals who have not received the antibiotic ([name], personal communication). Because of the concern of possible AMR, we will monitor its prevalence closely in this trial, before, during and after the intervention and both among those receiving and those not received MDA with the study drugs.

3.05. Distribution of the results

The results will be distributed and discussed with the local community, Malian health researchers, regional and national level representatives of the Ministry of Health in Mali and the World Health Organization. Main findings will be published in international peer-reviewed journals.

The study material will also be used for post-graduate training of Malian and Finnish students.

4. The study

4.01. Objectives of the proposed research

Primary objective:

1. To evaluate the impact of two azithromycin MDA regimens on infant mortality and other health outcomes, when provided in a context a rural West-African high-mortality context with an ongoing seasonal malaria chemoprevention (SMC) program.

Secondary objectives:

2. To evaluate the effect of alternative MDA frequencies on AMR and host microbiota composition
3. To investigate the feasibility of alternative azithromycin MDA strategies, including economic analysis
4. To test hypotheses that azithromycin MDA eliminates malaria parasitemia and reduces general and intestinal inflammation in asymptomatic children and to collect and store biological samples for assessing other possible mechanisms of azithromycin effect

4.02. Detailed study questions**Detailed questions on mortality (primary objective):**

- 1.1. Does biannual azithromycin MDA to 1-11 month (29-364 days) old infants, when provided quarterly during non-malaria season, reduce their mortality in a Mali-like setting, in which there is a functional SMC program
- 1.2. Does quarterly azithromycin MDA, provided throughout the year (i.e., 4 doses / year) to 1-11-month-old infants reduce their mortality in a Mali-like setting?
- 1.3. Does quarterly MDA have a bigger mortality effect than biannual MDA?
- 1.4. Do the following factors modify the effect of azithromycin MDA on mortality? (Exploratory analysis)
 - a. Infant age at the time of MDA (1-5 months vs 6-11 months)
 - b. Infant weight-for-age, length-for-age, weight-for-length at the time of MDA
 - c. Infant sex
 - d. Season of MDA dosing (malaria versus non malaria season) and SMC implementation in village (SMC given versus SMC not given)
 - e. Cluster level coverage of SMC
 - f. Cluster level baseline mortality (established at first census)
 - g. Cluster and individual level coverage and number of administered azithromycin MDA doses
 - h. District of residence
 - i. Distance from the nearest health facility
 - j. Household asset or income index
 - k. Household WASH index
 - l. National outreach strategy category (standard/advanced)
 - i. There is an existing national outreach strategy (*Strategie Avancée*) in place to target communities that have limited access to healthcare. Inclusion into that strategy will be treated as a potential effect modifier.
 - m. Hard-to-reach village status assessed by the field workers
 - i. In addition to objective measures (geographical location distance to health facilities) and existing national assessment (*Strategie Avancée*), we will conduct a survey among field workers to obtain a subjective assessment on how difficult the village is to reach. The results will be summarized to a composite variable that will be used as a dichotomous variable on whether or not the village is “hard-to-reach”.

- 1.5. Does biannual or quarterly azithromycin MDA to 1–11-month-old infants reduce mortality among 12–59-month-old children living in the same communities (exploratory analysis)
- 1.6. Are hard-to-reach communities more likely to experience higher mortality than those within closer proximity or easier access to urban locations and health facilities (exploratory analysis)
- 1.7. Are communities under Strategie Avancée more likely to experience higher mortality than those in standard national outreach category (exploratory analysis)

Detailed questions on other health outcomes (primary objective):

- 1.8. Does biannual or quarterly azithromycin MDA to 1–11-month-old infants reduce the prevalence of ARI, diarrhea, or malaria symptoms among them?
- 1.9. Does biannual or quarterly azithromycin MDA to 1–11-month-old infants improve their weight gain, linear growth (length), or nutritional status (assess by Mid upper-arm circumference MUAC, weight-for-height-Z-score WHZ, Length-for-age Z-score LAZ, Weight-for-age Z-score WAZ)?

Detailed questions on AMR (secondary objective):

- 2.1. Does biannual or quarterly azithromycin MDA to 1–11-month-old infants cause an increase in the prevalence of phenotypic azithromycin resistance among *S. pneumoniae*, or *E. coli* strains isolated from 4–14-month of infants one year after the intervention has stopped?
- 2.2. What is the impact of biannual or quarterly azithromycin MDA to 1–11-month-old infants on the prevalence of azithromycin resistance among *S. pneumoniae* or *E. coli* strains isolated from 49–59-month-old children, who live in the same Malian communities but have not received azithromycin MDA, during and after the intervention period?
- 2.3. Does azithromycin resistant bacteria persist in individual children who received 1–4 doses of azithromycin 1 year after azithromycin MDA has stopped?
- 2.4. Does azithromycin resistant bacteria persist in individual children who received 1–4 doses of azithromycin 1 year after their azithromycin MDA has stopped but village MDA intervention has continued?
- 2.5. What is the impact of biannual or quarterly azithromycin MDA to 1–11-month-old infants on the diversity and composition of their intestinal microbiota and prevalence of azithromycin resistance genes in intestinal bacteria?

Detailed questions on feasibility including economic analysis (secondary objective):

- 3.1 Is scaling-up of azithromycin MDA as a national program to reduce mortality among 1–11-month-old infants feasible in Mali according to stakeholders?
- 3.2 What are the factors that need to be considered for various scaling-up strategies?
- 3.3 What is the level of feasibility, inter-rate reliability, and validity of an instrument targeted to capture a subjective assessment of hardness-to-reach amongst the field workers?
- 3.4 Is there an association between hard-to-reach village status and advanced national outreach strategy status (exploratory analysis)

Detailed questions on mechanisms of azithromycin action (secondary objective):

- 4.1 Does azithromycin MDA reduce malaria prevalence and parasite density, and increase blood hemoglobin concentration among 1–11-month-old infants?
- 4.2 Does azithromycin MDA reduce general inflammation (plasma C-reactive protein concentration) among 1–11-month-old infants?
- 4.3 Does azithromycin MDA reduce intestinal inflammation (concentration of Alpha-1-antitrypsine, neopterin, and myeloperoxidase from stool sample) among 1–11-month-old infants?

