4.19. Stratégie Avancée and field workers' assessment of hard-to-reach areas

Villages under Stratégie Avancée will be identified by the local field supervisors from the records maintained by the local districts and health areas. The Stratégie Avancée status information will be appended to the study data prior to the analysis by the study data manager.

We will conduct a survey amongst the trial data collection staff to obtain a subjective assessment on what is the geographical accessibility of a village. The overarching aims of the survey for the data collectors would be to develop an instrument to assess the hardness-to-reach from the point of view of data collectors or health care workers going to the locations, and to evaluate whether hardness-to-reach modify the effectiveness of LAKANA intervention. The survey will be implemented as an electronic questionnaire and the survey will be anonymous: no staff name or position will be recorded.

The participants will be approached by their field supervisors with an announcement of an invitation to fill the questionnaire based on their own experiences. Filling the questionnaire will be voluntary, but they will be informed on the benefits of what such information can provide: insight on their challenges during the data collection, an improved viewpoint on the collected trial data with hardness-to-reach as a predictor or effect modifier on the trial outcomes, and information that could improve the planning of future interventions that could help even the most remote communities.

The participants will be asked to fill the questionnaire before synchronizing the tablets for data collection, either at the beginning of the day or at the end of the day, at their convenience. The questions will be in French language, and at the beginning of the questionnaire, there will be a brief introduction and instructions on filling the electric form.

The form will consist of 12 questions for a single village. Each field worker will fill the form for 10 villages. The questions will be multiple choice questions and filling the form for one village will take approximately 5 minutes.

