The expected number of answers will be 75% of the available field workers. The field supervisors will be reminded to ask the field workers to fill the form until 75% is reached, or until the field supervisors report that there are no more field workers who are willing to fill the form. As the data collectors enter villages in teams, there are multiple data

collectors who have experience from a single village. Each village should be assessed by the full team of field workers, that is, each village should have at minimum two assessment by separate field workers.

There will be multiple survey rounds: the survey will be tested with 5 data collectors to assess the workload filling the forms for multiple villages, and to assess the data quality. If the data quality suffers from the workload of filling the questionnaire for many villages, the length of the electronic data capture form will be reduced by allowing the field workers to continue form filling at the later time.

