5.05. Subgroup analyses

For hypothesis generating purposes, we plan to carry out exploratory tests for interaction between the MDA intervention and the selected baseline variables, using the mortality and growth outcomes. Tests of hypotheses concerning intervention effects in these subgroups will be performed only if the interaction tests give statistically significant results ($p<0.1$).

The following variables would be assessed potential effect modifiers

1. Infant age at the time of MDA (1-5 months vs 6-11 months)
2. Infant weight-for-age, length-for-age, weight-for-length at the time of MDA
3. Infant sex
4. Season of MDA dosing (malaria versus non malaria season) and SMC implementation in village (SMC given versus SMC not given)
5. Cluster level coverage of SMC
6. Cluster level baseline mortality (established at first census)
7. Cluster and individual level coverage and number of administered azithromycin MDA doses
8. District of residence
9. Distance from the nearest health facility
10. Household asset or income index
11. Household WASH index
12. National outreach strategy category (standard/advanced)

13. Hard-to-reach village status assessed by the field workers

6. Ethical considerations

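### The hard-to-reach composite is cut to yes/no, with no stated cut-point, before the exploratory effect-modifier test; a graded score would keep information that the split discards

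*Combined protocol and SAP*

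**What the plan says.** - **Section 4.02, question 1.4 m** describes a field-worker survey on how difficult each village is to reach, and then states: "The results will be summarized to a composite variable that will be used as a dichotomous variable on whether or not the village is" hard to reach. This is the only place where the binary form is explicit.
- **Section 4.19** describes the raw material: "The form will consist of 12 questions for a single village. Each field worker will fill the form for 10 villages". On format: "The questions will be multiple choice questions". On replication: "each village should have at minimum two assessment by separate field workers". The number of answer options and the scoring are not given, nor whether all 12 questions enter the composite.
- **Section 5.05, item 13** lists the modifier as "Hard-to-reach village status assessed by the field workers". Subgroup effects are tested only if the interaction test reaches p<0.1.
- **Question 1.6** (section 4.02) uses the concept as a predictor: "Are hard-to-reach communities more likely to experience higher mortality than those within closer proximity". Question 3.4 asks about its association with the national outreach category. Both are phrased as a status. Section 4.19, in contrast, speaks of "hardness-to-reach as a predictor or effect modifier on the trial outcomes" without saying binary.
- No section gives a cut-point, a rule for raters who fall on opposite sides of it, or an analysis of the uncut composite.
- Questions 1.4, 1.6 and 3.4 are labelled exploratory, and section 5.05 describes the interaction tests as hypothesis-generating.

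**The concern.** A composite of 12 multiple-choice answers averaged or summed over two or more raters is naturally graded. Cutting it in two treats all villages on one side of the cut as alike. If mortality or the azithromycin effect shifts gradually with accessibility, part of the signal is thrown away before a test that is already weak, as interaction tests on mortality are. Because that test is the gate to any subgroup estimate, a missed gradient ends the analysis.

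The open cut is a second, smaller matter. The version history dates the survey to version 7 (13.11.2024), years after the trial was planned to start. The result can depend on where the cut falls, and nothing in the text fixes it.

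The plan also holds a binary accessibility measure already, the standard/advanced outreach category (1.4 l). Gradation is one thing that a 12-question survey can offer beyond it. Neighbouring modifiers such as distance to a health facility, the asset index and the WASH index carry no stated dichotomy.

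**Working it through.** The documents give no power or efficiency figure for this analysis, so there is nothing to reproduce. Two things can be worked out.

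**1. Information kept by a yes/no split when the relation is linear**

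This is the squared correlation between split and score. With p the share of villages called hard to reach:

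- General form: r² = p(1−p) × (difference between the two group means)² / variance of the score.
- Normal score, cut at c: r² = φ(c)² / [p(1−p)].

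Normal score:

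| p | φ(c) | r² | Lost |
|---|---|---|---|
| 0.50 | 0.399 | 0.637 (= 2/π) | 36% |
| 0.30 | 0.348 | 0.576 | 42% |
| 0.20 | 0.280 | 0.490 | 51% |
| 0.10 | 0.175 | 0.342 | 66% |

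Uniform score: the group means differ by 0.5 at any cut and the variance is 1/12. At the median r² = 0.25 × 0.25 × 12 = 0.75, so 25% is lost. At p = 0.20, r² = 0.16 × 0.25 × 12 = 0.48, so 52% is lost.

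Other shapes, by Monte Carlo, each at its own best cut:

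| Shape | Lost at best cut |
|---|---|
| U-shaped, beta(0.5, 0.5) | 19% |
| Two-humped, modes 3-4 SD apart | 21-28% |
| Mildly skewed, beta(2, 5) | 32% |
| Exponential | 35% |
| Lognormal (one shape tried) | 39% |
| 12 four-option items × 2 raters, inter-item correlation 0.9 down to 0.1 | 23-35% |

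The simulated 12-item scores lose about 28-52% at a 20% cut. The exponential score, whose best cut is near 20%, loses 52% at the median. A badly placed cut therefore usually costs more, in whichever direction it is misplaced.

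**2. What this could mean for power (illustration for question 1.6)**

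Inputs from section 5.04: 1150 clusters; 6 × 35,650 + 28,520 + 17,820 = 260,240 intervals, which agrees with the stated 260,200; allocation 3 : 4 : 2 (control : biannual : quarterly); rates 20, 16 and 12 per 1000; k = 0.1. Assumed, with no source in the documents: a normal score and a log-rate slope of 0.09 per SD.

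- Person-years: 260,240 / 4 = 65,060.
- Deaths: 65,060 × (3×0.020 + 4×0.016 + 2×0.012) / 9 ≈ 1,070.
- Information on the slope: I = D / (1 + k²D/C) = 1,070 / (1 + 0.01 × 0.93) ≈ 1,060.
- Power at two-sided 5% ≈ Φ(0.09 × √(I × r²) − 1.96).

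That calculation takes every village as rated. The survey may not reach that. Section 7.05 has 180 data collectors and section 4.19 expects 75% of field workers to respond, for 10 villages each, with at least two ratings per village: 180 × 0.75 × 10 / 2 = 675 villages (900 at full response), unless further survey rounds add more. With 675 villages of average size, D ≈ 1,070 × 675/1150 = 628 and I ≈ 622.

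| Villages rated | Score | Median split | 20% cut |
|---|---|---|---|
| 1150 | 83% | 65% | 54% |
| 675 | 61% | 43% | 35% |

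A Poisson simulation with 1150 villages (400 runs, error about 2-2.5 points) gave 84%, 64% and 54%, matching the first row. The same simulation for the interaction test at p<0.1, with an assumed slope difference of 0.17 per SD and the two azithromycin arms pooled, gave about 86%, 68% and 63%.

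**The case against.** The strongest case for leaving the text alone has four parts.

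- **The instrument is new.** Its reliability and validity are themselves study question 3.3. Entering an unvalidated subjective sum as linear per SD assumes an approximately interval scale. This stands, and it is why the score needs a non-linearity check.
- **A step is possible.** If risk changes abruptly at the chosen cut, the binary form loses little or nothing and can do better. This also stands, but no cut or threshold is given that would make a step the working assumption.
- **Accessibility is also covered elsewhere.** Distance to the nearest health facility is a separate modifier with no stated dichotomy, and a status suits the phrasing of questions 1.6 and 3.4. The survey is meant to add to the objective measures, however, so this limits the loss without removing it. Nor does it follow that a second binary is worthless: question 3.4 exists to compare it with the national category.
- **The consequence is small.** This is one of 13 exploratory modifiers, and no primary, secondary or safety conclusion rests on it. This stands in full.

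A reader might also infer more than the documents support:

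- *That at least a third of the information is always lost.* That holds for a normal score at any cut, but several other plausible shapes lose less at their best cut, and the documents give no score distribution.
- *That scoring would bring these tests to 80% power or more.* The slopes are assumptions, full rating of 1150 villages is not assured, the calculations use equal-sized clusters where the plan expects unequal ones, and the plan allows pooling of the azithromycin arms only for the mechanism hypotheses (12-14 in section 5.01).
- *That the plan dichotomises everywhere.* It says so only under 1.4 m; for 1.6 and 3.4 the binary form is implied by wording.
- *That the cut will be chosen from the results.* Nothing shows this. The cut is simply not stated.

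**Conclusion.** The point holds as a low-cost improvement to an exploratory analysis. Under 1.4 m, and by its label in section 5.05 item 13, a multi-item, multi-rater composite is reduced to yes/no with no stated cut and no analysis of the score itself.

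The size depends on two unknowns: the shape of the score and the form of the relation. Given a graded, roughly log-linear relation, the loss is about 36% at best for a normal score and about 20-35% at best for most other shapes tried (39% for the lognormal one), usually rising when the cut is poorly placed. Given a step at the cut, the loss is little or nothing. In power terms, the question 1.6 illustration shows a gap of about 18 points between score and median split with either 1150 or 675 villages rated, but the absolute levels rest on an assumed slope and should not be quoted as expected power. The primary comparison is unaffected.

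**What to change.** - **1.4 m and section 5.05 item 13:** enter the composite as a village-level score (standardised, linear) in the interaction test, with a pre-stated check for non-linearity.
- **Questions 1.6 and 3.4:** where the same variable is used, analyse it in the same form for the predictor and association tests.
- **Yes/no status:** keep it for tables and for displaying subgroup estimates.
- **Before linkage to mortality data:** write down which questions enter the composite, how they are scored, how raters are combined, how villages with fewer than two ratings are handled, and where the cut lies.

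The cost is SAP wording only; the questionnaire and field work do not change. The downside is that an effect per SD is less direct for programme staff and leans on an approximately interval scale. The retained yes/no display answers the first and the non-linearity check the second.
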